8.4 UNANTICIPATED PROBLEMS

8.4.1 DEFINITION OF UNANTICIPATED PROBLEMS

See DSMP above for detail

8.4.2 UNANTICIPATED PROBLEMS REPORTING

See DSMP above for detail

8.4.3 REPORTING UNANTICIPATED PROBLEMS TO PARTICIPANTS

N/A

9 STATISTICAL CONSIDERATIONS

9.1 STATISTICAL HYPOTHESES

Aim 1: Test the efficacy of the intervention in slowing adiposity and weight gain trajectory and improving health behaviors (nutrition and physical activity) in 4-year-old Hispanic children from Time 1 (0 months [baseline]) to Time 2 (9 months [completion of the intervention]) and Time 1 to Time 3 (15 months [after 6 months with no contact from the study staff]).

Aim 2: Test the efficacy of the intervention in decreasing adiposity and weight and improving health behaviors and self-efficacy in overweight or obese Hispanic mothers from Time 1 to Time 2 and from Time 1 to Time 3.

Primary outcomes include slowing of child adiposity (waist circumference and triceps and subscapular skinfolds) and weight gain (BMI percentile) trajectory and a decrease in mother's adiposity and weight (BMI). We hypothesize that intervention group children will slow the trajectory of adiposity and weight gain and intervention group mothers will decrease adiposity and weight significantly more than the control group.

Secondary outcomes include child and mothers health behaviors (nutrition and physical activity) and mother's self-efficacy (nutrition and physical activity). We hypothesize that intervention group children and mothers will improve health behaviors and mothers will improve self-efficacy significantly more than the control group.

Aim 3: Identify the mediators through which the intervention influences the trajectory of adiposity and weight gain in children and decrease in adiposity and weight in mothers. We hypothesize that health behaviors and self-efficacy may mediate adiposity and weight loss in mothers and nutrition and physical activity behaviors in children may mediate a slower adiposity and weight gain trajectory.

Aim 4: Calculate the cost of implementing the intervention for public health departments and the costs for mothers participating, from Time 1 to Time 2 and compare these costs to the outcomes of the intervention (cost-effectiveness) and the potential economic benefits of these outcomes (cost-benefit analysis). We hypothesize that the intervention is primarily focused on knowledge and behaviors in an at-risk population and may be cost-effective in comparison with other approaches to managing overweight and obesity.

Exploratory Aim: Determine whether intervention group mothers in the overweight versus obese BMI category benefit equally from the intervention in adiposity, weight, health behaviors, and self-efficacy.

9.2 SAMPLE SIZE DETERMINATION

A total of 250 mother-child dyads, or 125 dyads in each randomized group, are expected to complete the study. However, we will enroll 294 mother-child dyads ($n = 588$ participants) or 147 dyads per group, to take into account a 15% attrition rate. Our previous studies with Hispanic mothers with limited English proficiency and their children have had attrition rates ranging from 9% to 15% [23, 33]. Power calculations were performed with POWERLIB20 SAS/IML modules, which incorporate methods described in Muller [39]. These methods calculate power for a general linear multivariate model that includes repeated measures data structures, of which a two-group longitudinal design is a special case. Power was calculated on the use of a separate multivariate model for each outcome addressed in the aims, incorporating measurements at all available time points. Effect size estimates were based on the pilot data [23], where estimated within-subject correlation and standardized mean difference were .25 and .53, respectively, for mothers' BMI and .30 and .59, respectively, for children's BMI percentiles. For each outcome, power was computed for a test of the time by treatment interaction at a two-sided significance level of .05. For an analyzable sample of 125 mother-child dyads per group (total of 250 mother-child dyads), calculated statistical power exceeds 95% for both the test of children's BMI percentiles in Aim 1 and the test of mothers' BMI in Aim 2; if the within subject correlations and standardized mean differences are lower than observed in the pilot at .20 and .45, respectively, statistical power will nonetheless exceed 80%. A formal power analysis was not conducted for Aim 3 because the focus is on estimation (rather than testing) of direct and indirect mediation effects. Nonetheless, based on Shrout and Bolger [40], a sample size of 80 to 85 should provide power in the 70% to 85% range to detect medium effects of the intervention on the mediator (e.g., maternal self-efficacy), and the mediator on the outcomes (e.g.,

mother's BMI) with a two sided .05 significance level. Our 250 dyads should provide an adequate sample to quantify mediation of the relevant variables.

9.3 POPULATIONS FOR ANALYSES

Means, standard deviations, minimums, medians, and maximums will be determined for each continuous variable; frequencies and percentages will be tabulated for each categorical variable. Preliminary analyses will be performed to determine whether, despite randomization, the intervention and control groups were unbalanced on gender, age, or income. Any variable with an imbalance between the groups at baseline will be examined to determine whether it is related to any of the outcome variables. If significant relationships are identified, the variable will be included as a covariate in the models for the affected outcome(s) as a potential confounder. An intent-to-treat analysis will be used in which all subjects are included in the analysis and analyzed according to their initial randomized assignment.

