9.4 STATISTICAL ANALYSES

- 9.4.1 GENERAL APPROACH
- 9.4.2 ANALYSIS OF THE PRIMARY ENDPOINT(S)
- 9.4.3 ANALYSIS OF THE SECONDARY ENDPOINT(S)
- 9.4.4 SAFETY ANALYSES
- 9.4.5 BASELINE DESCRIPTIVE STATISTICS
- 9.4.6 PLANNED INTERIM ANALYSES
- 9.4.7 SUB-GROUP ANALYSES
- 9.4.8 TABULATION OF INDIVIDUAL PARTICIPANT DATA
- 9.4.9 EXPLORATORY ANALYSES 9.5
- 9.4.10 DATA ANALYSIS

Aim 1: To test the efficacy of the intervention in decreasing trajectory of adiposity and weight gain in 4-year-old children, separate mixed models will be used to test longitudinal differences between the intervention and control group means for each outcome across the study period. Mixed effects models, with a random intercept to account for between-mother or between-child differences, will be used for repeated measures analyses of each outcome (child BMI percentile, waist circumference, and triceps and subscapular skinfolds). The dependent variable will be the outcome at each of the three time points; the model will include time point (categorical), intervention group, and the interaction between the two. A test of this interaction will serve as the overall test of intervention effect, and step-down tests will be conducted to compare Time 2 and Time 3 to Time 1, and to estimate how or whether the intervention effect changed from Time 2 to Time 3, using a Hochberg correction to account for multiple comparisons [41, 42]. Results will be summarized through the least-squares means for each group at each time point and the mean difference and corresponding 95% confidence interval.

Aim 2: To test the efficacy of the intervention in decreasing adiposity and weight in mothers, we will fit mixed models analogous to those described for Aim 1 with each of the primary outcomes (mother's BMI and adiposity measures: waist circumference, and triceps and subscapular skinfolds) and secondary outcomes (child health behaviors: nutrition and physical activity, mother's health behaviors: nutrition and physical activity, and mother's self-efficacy: nutrition and physical activity).

Aim 3: To identify the mediators through which the intervention influences weight management in mother-child dyads, the approach of Shrout and Bolger [40] will be employed. This method, based on bootstrapping, builds on established mediation testing procedures, such as the Baron and Kenny approach [43] and the Sobel test [44]. Mediation analyses test pathways by which an explanatory variable (X) is theorized to influence the

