Exploratory Aim: Analyses will be performed on weight status, adiposity, health behavior, and self-efficacy to explore whether the intervention effects for mothers are similar for those who are overweight (BMI 25-29.9kg/m²) and those who are obese (BMI ≥ 30 kg/m²). The mixed models described for Aims 1 and 2 will be implemented for each of the weight status, adiposity, health behavior, and self-efficacy variables, with the addition of four explanatory variables to each model: an indicator for the obese group, the interaction between this indicator and the indicator variable for group membership, the interaction between this indicator and time, and the three-way interaction among the group indicator, obese indicator, and time. The hypothesis test for the three-way interaction as well as the obesity indicator by group indicator interaction jointly equal to zero will indicate whether the intervention effects are homogeneous across BMI ranges. For each outcome, differences will be calculated to test the effects of the intervention versus control group at each follow-up point separately for each BMI range. Similar analyses will be performed with groupings of children in the 25th-84.9th percentile (normal weight), 85th-94.9th percentile (overweight) and $\geq 95^{\text{th}}$ percentile (obese).

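### Section 9.3 chooses covariates from observed imbalance and significance and states no covariate-by-time term, so the adjustment as written would not correct the group-by-time test

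*Combined protocol and SAP*

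**What the plan says.** Section 9.3 sets a two-step rule. Step one: "Preliminary analyses will be performed to determine whether, despite randomization, the intervention and control groups were unbalanced on gender, age, or income". Step two: "Any variable with an imbalance between the groups at baseline will be examined to determine whether it is related to any of the outcome variables". A variable that passes both steps enters the model: "If significant relationships are identified, the variable will be included as a covariate in the models for the affected outcome(s) as a potential confounder". The section gives no threshold for imbalance, does not say whether age means the mother's or the child's, and does not say in what form the covariate enters.

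Section 9.4.10 (Aim 1, applied by analogy to Aim 2) takes the outcome at each of the three time points as the dependent variable, so Time 1 is one of the modelled outcomes. On the fixed effects: "the model will include time point (categorical), intervention group, and the interaction between the two". On the covariance: "Mixed effects models, with a random intercept to account for between-mother or between-child differences". On the test: "A test of this interaction will serve as the overall test of intervention effect". On reporting: "Results will be summarized through the least-squares means for each group at each time point and the mean difference and corresponding 95% confidence interval".

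The Exploratory Aim in the same section lists its time interactions one by one, among them "the interaction between this indicator and time". Section 9.3 lists none for its covariates. The sensitivity paragraph puts site in all models and plans a look at differential effects by site or cohort.

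**The concern.** There are two linked problems. First, the model for each outcome depends on what this trial's data show, so covariate sets can differ between outcomes and are fixed only after the data are seen. The second screen also reads as a relation to the outcome, not to change in it. A variable related only to level can pass although it cannot bias a change contrast, and one related only to change can fail.

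Second, the natural reading of the rule adds the covariate without a time interaction. The tested quantity is the difference between arms in change from Time 1, and a covariate whose effect is the same at every visit cannot alter it. If child age, say, is unbalanced and predicts change in waist circumference, the team would report an adjusted analysis whose test still carries the imbalance. The least-squares means would move while the test beside them would not, and a reader could take the test as adjusted.

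**Working it through.** **Inputs from the documents.** 125 dyads per arm analysable, 15% attrition, two-sided .05, pilot within-subject correlation and standardized difference of .25 and .53 (mothers) and .30 and .59 (children), and a lower case of .20 and .45 (9.2); model and test (9.4.10); all available data used (9.4.10, sensitivity paragraph).

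**Assumed, because the documents give no values.** Covariate imbalance .3 SD; covariate effect .3 at Time 1, drifting by 0 or .3 by Time 3; imbalance judged at p<.05; the share R² of the variance in change that the covariate explains.

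**1. The plan's own figure.** For the 2-df group-by-time test under compound symmetry with arm differences (0, d, d), λ = (n/2) × Σ(d_t − d̄)² / (1 − ρ), with Σ(d_t − d̄)² = 2d²/3.
- Mothers: 62.5 × .1873/.75 = 15.6, power .951.
- Children: 62.5 × .2321/.70 = 20.7, power .987.
- Lower case: 62.5 × .135/.80 = 10.5, power .834.

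The statements of above 95% and above 80% reproduce under this assumed pattern. A linear pattern (0, d/2, d) would give .873, .950 and .710. No covariate enters these formulas, so the present point does not touch them.

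**2. Algebra.** Write y_it = α_t + β_t g_i + δ c_i + b_i + e_it, with c_i constant over time. Then y_i3 − y_i1 = (α_3 − α_1) + (β_3 − β_1) g_i + (e_i3 − e_i1). The term δ c_i has gone. If the effect varies by visit (δ_t), then (δ_3 − δ_1) c_i remains, and its difference between arms is imbalance × drift: .3 × .3 = .09 SD of spurious effect. With zero drift there is nothing to correct.

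**3. Fits, complete data.** In one restricted-maximum-likelihood fit, the two group-by-time estimates were .129138 and .003628, each with standard error .149709, both without the covariate and with it added without a time interaction. The baseline group coefficient moved from .205 to .027. Adding covariate by time gave .072 and −.123.

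**4. Repeated fits.** 400 data sets per case, 125 per arm, ρ = .25, drift .3. The table gives the mean spurious Time 3 effect in SD.

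| Data | No covariate | Covariate only | Covariate + covariate × time |
|---|---|---|---|
| Complete | .097 | .097 | .006 |
| 15% random dropout | .0827 | .0833 | −.0068 |
| Dropout depending on covariate | .0696 | .0776 | −.0074 |

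Under random dropout the covariate alone moved a single trial's estimate by .014 on average and .056 at most, against a standard error of .163. Under covariate-dependent dropout the largest shift was .067. With complete data the standard error is √(2 × .75) × √(2/125) = .1549, and .1567 with covariate by time.

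**5. False-positive rate given imbalance.** For a single change contrast, if the covariate's z for imbalance is z, the test statistic is approximately N(√R² · z, 1 − R²). Given |z| > 1.97, the mean of |z| is φ(1.97)/(1 − Φ(1.97)) = 2.35. At R² = .10: √.10 × 2.35 = .743 and √.90 = .949. The upper tail is P(Z > (1.96 − .743)/.949 = 1.28) = .100, the lower tail is .002, total about 10%. Integrating over z instead of using its mean gives 5.5%, 7.7%, 10.3% and 15.8% at R² of .01, .05, .10 and .20. Simulation of 40,000 trials gave 7.8%, 10.3% and 15.6% for the last three, and 4.8%, 4.4% and 5.6% with covariate by time.

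**6. Overall rate.** At R² = .10 the rate is 4.7% when the covariate is not unbalanced. Imbalance by this cut-off has probability .049, so the overall rate is .049 × .103 + .951 × .047 = .050.

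**7. How often imbalance arises.** For three independent variables at .05 (child models), 1 − .95³ = 14%. In mother models gender is constant, so 1 − .95² = 9.8%.

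**The case against.** The strongest reply is that Section 9.3 says only that the variable becomes a covariate and never says it enters without a time interaction. That stands. A reader might infer that the plan prescribes main effects only, but the documents do not say so. It is the natural reading, because time interactions are spelled out for the Exploratory Aim and not here, and under either reading the text has to be settled.

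A reader might also infer that the trial's type I error is inflated. It is not: randomization holds it at about 5% across all trials, and the higher rates apply only to trials in which an imbalance has occurred. Those rates also rest on assumed R². At .01 the excess is negligible, and child BMI percentile is already referenced to age and sex, so a large R² for those two variables would need justification for that outcome. Waist circumference and skinfolds do not have that protection.

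Three further points stand. A covariate whose effect is constant over time needs no correction. Exact cancellation requires complete data. And the adjustment is not inert, since it changes the least-squares means. A claim that precision is being lost is not supported: no gain was shown, and in the imbalanced case the standard error rose slightly. The look at differential effects by site goes beyond a simple site term, but the plan does not say whether the primary models include site by time.

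**Conclusion.** The point holds in limited form. Covariates are selected from the trial's own data, and as the rule is written, with no time interaction stated, the adjustment would leave the group-by-time test unchanged with complete data and without useful net correction at 15% dropout. In the assumed case of .3 SD imbalance and .3 drift, a spurious effect of about .09 SD stays in the test, and a covariate-by-time term removes nearly all of it. Given imbalance at p<.05, the false-positive rate is about 5.5% to 16% for R² from .01 to .20. The size therefore depends on R² for change, which the documents do not give. Overall type I error, the stated power and the sample size are not affected. The change is cheap and should be made before the data are analysed.

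**What to change.** In 9.3, delete the imbalance screen and the significance screen. Replace them with a fixed list: child age, sex and household income in the child models; mother's age and income in the mother models. State that each enters every model with its interaction with categorical time, whatever the observed balance. Baseline tables can stay as description. In 9.4.10, add these terms to the model statement for Aims 1 and 2, and state whether site, already in all models, also has a time interaction.

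The cost is a few degrees of freedom per model, a slightly larger standard error when a covariate happens to be unbalanced (.1549 to .1567 in the assumed case above), and a rule set in advance for missing income values so that no dyad leaves the intention-to-treat analysis.

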9.4 STATISTICAL ANALYSES

- 9.4.1 GENERAL APPROACH
- 9.4.2 ANALYSIS OF THE PRIMARY ENDPOINT(S)
- 9.4.3 ANALYSIS OF THE SECONDARY ENDPOINT(S)
- 9.4.4 SAFETY ANALYSES
- 9.4.5 BASELINE DESCRIPTIVE STATISTICS
- 9.4.6 PLANNED INTERIM ANALYSES
- 9.4.7 SUB-GROUP ANALYSES
- 9.4.8 TABULATION OF INDIVIDUAL PARTICIPANT DATA
- 9.4.9 EXPLORATORY ANALYSES 9.5
- 9.4.10 DATA ANALYSIS

Aim 1: To test the efficacy of the intervention in decreasing trajectory of adiposity and weight gain in 4-year-old children, separate mixed models will be used to test longitudinal differences between the intervention and control group means for each outcome across the study period. Mixed effects models, with a random intercept to account for between-mother or between-child differences, will be used for repeated measures analyses of each outcome (child BMI percentile, waist circumference, and triceps and subscapular skinfolds). The dependent variable will be the outcome at each of the three time points; the model will include time point (categorical), intervention group, and the interaction between the two. A test of this interaction will serve as the overall test of intervention effect, and step-down tests will be conducted to compare Time 2 and Time 3 to Time 1, and to estimate how or whether the intervention effect changed from Time 2 to Time 3, using a Hochberg correction to account for multiple comparisons [41, 42]. Results will be summarized through the least-squares means for each group at each time point and the mean difference and corresponding 95% confidence interval.

Aim 2: To test the efficacy of the intervention in decreasing adiposity and weight in mothers, we will fit mixed models analogous to those described for Aim 1 with each of the primary outcomes (mother's BMI and adiposity measures: waist circumference, and triceps and subscapular skinfolds) and secondary outcomes (child health behaviors: nutrition and physical activity, mother's health behaviors: nutrition and physical activity, and mother's self-efficacy: nutrition and physical activity).

Aim 3: To identify the mediators through which the intervention influences weight management in mother-child dyads, the approach of Shrout and Bolger [40] will be employed. This method, based on bootstrapping, builds on established mediation testing procedures, such as the Baron and Kenny approach [43] and the Sobel test [44]. Mediation analyses test pathways by which an explanatory variable (X) is theorized to influence the

mediator (M), which in turn influences the outcome (Y). Models will be conceptualized for each measure of weight and adiposity for mothers identified in Aim 1 (Y) and for each proposed mediator (M), relative to the randomized intervention group (X). For each model, an effect ratio (defined as the ratio of the indirect effect to the total effect, yielding the proportion of the effect that is mediated) and its bootstrapped distribution will be computed to assess the strength of mediation. Mediators (M) to be tested are improvements in health behaviors and self-efficacy. For example, we will analyze the effect of the intervention on change in maternal self-efficacy from baseline to Time 2, and, in turn the effects of this change in maternal self-efficacy at Time 2 on change in maternal BMI at Time 3.

Sensitivity analyses for Aims 1-3. Site will be included in all the models, and we will look for evidence of differential effects across cohort or site. The primary analyses use all available data, but if there is evidence of differential missingness by treatment group, we will use imputation methods as a sensitivity analysis.

Aim 4: We will calculate the incremental cost-effectiveness of the intervention, carried out from society's perspective as:

$$CE_{ij} = \frac{C_i - C_j}{E_i - E_j}$$

Where C is cost over the time period of the study; E is effectiveness measured by the outcomes; *i* refers to the intervention and *j* refers to the control group. We will calculate cost-effectiveness for the principal outcomes of the study; including cost per unit of BMI reduction, and cost per unit of improvement on the nutrition and physical activity self-efficacy scales. We will carefully track and calculate the costs of the program intervention activities and the control group activities, in order to measure the differences between the costs in the two groups. These costs will include hiring interventionists for all aspects of the Healthy Mothers-Healthy Children intervention. We will track the time invested in the program by participants in both the intervention and control group and calculate the value of time (opportunity cost) relative to the mothers' average income.

Exploratory Aim: Analyses will be performed on weight status, adiposity, health behavior, and self-efficacy to explore whether the intervention effects for mothers are similar for those who are overweight (BMI 25-29.9kg/m²) and those who are obese (BMI ≥ 30 kg/m²). The mixed models described for Aims 1 and 2 will be implemented for each of the weight status, adiposity, health behavior, and self-efficacy variables, with the addition of four explanatory variables to each model: an indicator for the obese group, the interaction between this indicator and the indicator variable for group membership, the interaction between this indicator and time, and the three-way interaction among the group indicator, obese indicator, and time. The hypothesis test for the three-way interaction as well as the obesity indicator by group indicator interaction jointly equal to zero will indicate whether the intervention effects are homogeneous across BMI ranges. For each outcome, differences will be calculated to test the effects of the intervention versus control group at each follow-up point separately for each BMI range. Similar analyses will be performed with groupings of children in the 25th-84.9th percentile (normal weight), 85th-94.9th percentile (overweight) and $\geq 95^{\text{th}}$ percentile (obese).

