Data will be collected at Time 1 (0 months [baseline]), Time 2 (9 months [completion of the intervention]) and Time 3 (15 months [after 6 months with no contact from the study staff]). Time 2 data will determine the magnitude of the intervention effects after the intensive intervention and continued support; Time 3 data collection will test efficacy after the mother-child dyads have had sufficient time to implement their new nutrition, physical activity, and coping skills on their own. These times were chosen because 3 to 6 months after completion of an intervention represents a standard length of time for follow-up in weight reduction studies, and gives mothers and children the time necessary to make changes in health behaviors [19].

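### The plan's mixed models name a random intercept as the only within-person covariance; if correlation falls with time, the Time 3 versus Time 1 confidence interval is too narrow and a faded effect is too often called durable.

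*Combined protocol and SAP*

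**What the plan says.** Section 9.4 (9.4.10, Aim 1) plans "Mixed effects models, with a random intercept to account for between-mother or between-child differences". For the fixed effects, "the model will include time point (categorical), intervention group, and the interaction between the two". On inference, "A test of this interaction will serve as the overall test of intervention effect"; then "step-down tests will be conducted to compare Time 2 and Time 3 to Time 1", together with an estimate of how the effect moves between Time 2 and Time 3, "using a Hochberg correction to account for multiple comparisons". Results are to be reported with 95% confidence intervals. Aim 2 uses the same kind of model for the mothers' primary outcomes and for the secondary outcomes.

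Neither section 9.4 nor its sensitivity analyses name a residual covariance structure, a robust standard error, a degrees-of-freedom method or a fallback.

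The visits are unequally spaced (section 4.1): "Data will be collected at Time 1 (0 months [baseline]), Time 2 (9 months [completion of the intervention]) and Time 3 (15 months" after six months without staff contact.

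Section 9.2 rests on a different class of model: "Power was calculated on the use of a separate multivariate model for each outcome addressed in the aims". There, "power was computed for a test of the time by treatment interaction at a two-sided significance level of .05". It gives one correlation per outcome: .25 for mothers' BMI, .30 for children's BMI percentile, and .20 as a conservative case.

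**The concern.** A random intercept with independent residuals is compound symmetry. It applies one standard error to all three pairwise time contrasts, built from the average of the three change variances. If measurements further apart are less correlated, the 15-month change is really the most variable of the three and the 6-month change from Time 2 to Time 3 the least variable.

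Both errors favour a finding of durability. A lasting effect at Time 3 is declared too readily, and a loss of effect between Time 2 and Time 3 is detected too rarely. Aims 1 and 2 both name the Time 1 to Time 3 comparison, and section 4.1 presents Time 3 as the test of efficacy once families are on their own. The width of that interval therefore matters to the trial's message.

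**Working it through.** **Inputs from the documents.** 125 dyads per group analysed; 294 enrolled for 15% attrition; two-sided .05; visits at 0, 9 and 15 months; correlation and standardized difference of .25/.53 (mothers), .30/.59 (children) and .20/.45 (conservative).

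**Assumptions.** Equal variances; correlation decaying exponentially in months; the single documented correlation read as the 9-month value r. Section 9.2 does not say which interval that correlation spans. Values of .50 and .90 are added to show the range.

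**1. The plan's own figures.** 250/(1 - 0.15) = 294.1, so 294. For the 2-df interaction with one common correlation and effect pattern (0, d, d), the noncentrality is (n/2) x (2d²/3)/(1 - r).
- Mothers: 62.5 x 0.1873/0.75 = 15.6, power 95.0-95.1%.
- Children: 62.5 x 0.2321/0.70 = 20.7, power 98.7%.
- Conservative: 62.5 x 0.1350/0.80 = 10.5, power 83.2-83.4%.

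The ranges cover the multivariate and univariate F tests. The stated powers (over 95% and over 80%) reproduce.

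**2. Contrast variance.** For the group difference in change from visit a to visit b, the true variance is 4σ²(1 - ρab)/n. With complete data the random-intercept model uses 4σ² x mean(1 - ρ)/n for every pair. The ratio is k = (1 - ρab)/mean(1 - ρ), and the true size of a nominal 5% test is 2[1 - Φ(1.96/√k)].

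Example at r = .25: ρ13 = .25^(15/9) = .099 and ρ23 = .25^(6/9) = .397. The values of 1 - ρ are .750 (Time 1-2), .901 (Time 1-3) and .603 (Time 2-3), with mean .751. For Time 3 versus Time 1, k = .901/.751 = 1.20 and the size is 7.35%.

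| r (9 months) | k, T3-T1 | size T3-T1 | 95% CI coverage, T3-T1 | size T2-T1 | size T3-T2 |
|---|---|---|---|---|---|
| .20 | 1.17 | 6.99% | 93.0% | 5.05% | 3.11% |
| .25 | 1.20 | 7.35% | 92.7% | 4.98% | 2.87% |
| .30 | 1.23 | 7.67% | 92.3% | 4.91% | 2.67% |
| .50 | 1.32 | 8.82% | 91.2% | 4.60% | 2.04% |
| .90 | 1.47 | 10.59% | 89.4% | 4.02% | 1.27% |

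As r approaches 1, k tends to 15/10 = 1.5 and the size to 10.95%. With constant correlation k = 1 and the size is 5%.

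**3. Measurement noise.** At r = .90, noise making up 2%, 5% and 10% of the variance lowers the 10.6% to 9.7%, 8.8% and 7.8%.

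**4. Dropout.** A REML random-intercept simulation (3,000 trials, 147 per arm, 15% monotone dropout) gives 7.3% at r = .25 and 10.3% at r = .90.

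**5. The planned procedure.** Simulation of 40,000 trials per setting, reading the overall test as a gate followed by Hochberg over all three contrasts:
- No effect anywhere: overall test about 5-6%; Time 3 versus Time 1 rejected in 2.9-4.9%; any step-down rejection 4.4-5.3%.
- Effect of .45-.59 at Time 2 that is gone by Time 3: Time 3 versus Time 1 falsely rejected in 5.1-7.1% at r = .20-.30, 7.9-8.9% at .50 and 10.4-10.7% at .90. With constant correlation .25 and an effect of .53 it is 4.3%.

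**6. The alternative.** Testing the Time 3 minus Time 1 change on its own variance, as an unstructured covariance does with complete data, gives an unadjusted size of 4.9-5.2% in every setting.

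**The case against.** Four stronger readings are tempting, and the documents support none of them.

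- **That the trial's Time 3 claim has a 7-11% false-positive rate.** That is the size of one unadjusted contrast. The lead test is the interaction, at about 5-6%, and the planned Hochberg step-down holds the Time 3 claim to about 3-5% when nothing works. Excess error in the planned procedure needs a real Time 2 effect that has faded.
- **That the unequal visit spacing is to blame.** Equally spaced visits give almost the same figures (6.8% against about 7.4% at r = .25; 10.5% against 10.6% at .90). The driver is correlation that falls with lag.
- **That the plan commits to compound symmetry and excludes anything else.** It does not. It is silent on the residual structure, so a richer one may be intended.
- **That the power calculation fails because it used another model.** The stated power reproduces under a single common correlation, and N does not change.

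The size of the problem is also assumed. The documents give no lag-specific correlations, .90 is three times the largest documented value, and noise pulls the figure down. Time 2 versus Time 1 is essentially unaffected (about 4-5%).

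All of this stands, and it narrows the point. It does not answer the interval coverage, which Hochberg does not repair, or the faded-effect case, which the plan explicitly sets out to examine. If a richer covariance was intended, the plan still has to name it.

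**Conclusion.** The point holds as a weakness in the stated covariance. Followed as written, the model gives Time 3 versus Time 1 an interval that covers about 89-93% instead of 95%, and Time 3 versus Time 2 an interval that is too wide, provided correlation declines with lag. At the documented correlations the effect is modest: about 7-8% unadjusted, and about 5-7% for a false durability claim after a faded Time 2 effect. The upper figures of about 11% and 10.7% need a 9-month correlation near .90 and no measurement noise. With constant correlation there is no inflation. The direction rests only on decay with lag; the sizes rest also on the exponential form and equal variances. The overall test of intervention effect is little affected.

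**What to change.** For all Aim 1 and Aim 2 outcomes, replace the random intercept with an unstructured 3 x 3 within-person covariance over the three visits. Fit it by REML, with a named small-sample degrees-of-freedom method and a stated fallback if the model does not converge. Leave the fixed effects, the overall test and the Hochberg step-down as they are.

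The cost is a sentence in section 9.4 and six covariance parameters instead of two, a small burden with 250 dyads. The change is consistent with the multivariate model behind section 9.2, leaves N and stated power unchanged, and remains valid whether or not correlation decays.
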